Systolic function. Ejection fraction (EF) will be calculated from the M-mode measurements and from the volumes as calculated from the Biplane Simpsons analysis using the formula: EF (%) = 100 * (Diastolic Volume – Systolic Volume)/ Diastolic Volume

Assessment of LV diastolic function and LV filling pressures. Pulsed wave Doppler examination of mitral (before and with Valsalva maneuver) and pulmonary venous inflow as well as Doppler tissue imaging of the mitral annulus will be performed.

Analytic methods

Both plasma and urine concentration of lothalmate will be determined by the Mayo Core Renal lab. Glomerular filtration rate (GFR) will be calculated using lothalmate clearance using the following equation:

$$GFR \text{ (ml/min)} = \frac{U \times V}{P}$$

[Where: U = urine concentration; P = plasma concentration; V = urine flow (mL/min)]

Plasma and urine will be analyzed for sodium with the Beckman ion-selective analyzer. Urine creatinine will be measured by the Mayo Core Renal Laboratory. Renal cGMP generation, will calculated as follows: {[urine cGMP * urine flow] – [plasma cGMP * GFR]}. Venous blood for hormone analysis will be collected in heparin and EDTA tubes and immediately placed on ice. After centrifugation at 2,500 rpm at 4C, the plasma will be decanted and stored at -80C until analysis. Urine for cGMP radioimmunoassays will also be collected on ice as previously described.^{31,67} Specific radioimmunoassays include renin, aldosterone, angiotensin II, angiotensin 1-7 ANP, BNP, Bradykinin, NO and cGMP will be carried out in the co-investigator [name] laboratory, utilizing well established methodologies in the laboratory.⁶⁸ ACE and ACE 2 will be measured by high-performance liquid chromatography with electrochemical detection.

Potential risk and protection against risk

E. Human Subjects Research

This Human Subjects Research meets the definition of a clinical trial.

Human subject involvement and characteristic

The specific subject population is described in the Specific Methods for each protocol. The inclusion and exclusion criteria are listed in the Specific Methods. These protocols will not involve special classes of subjects, such as fetus, neonates, pregnant women, children, prisoners, institutionalized individuals, or others who may be considered vulnerable populations.

Source of materials

Plasma samples, urine samples echocardiographic data and clinical data will be used entirely for research purposes. Patient identifiers will not be released outside of Mayo and any publications will exclude any kind of patient identifiers that could be correlated with the specific patient.

Potential risks and Protection against risk

The overall risk for participation in this protocol is small and the main concern is that the addition of Candesartan (AT 1 blocker) and or increasing the ACE inhibitor dose would result in hypotension, hyperkalemia, and increased plasma creatinine. However, we demonstrated that acute AT1 receptor blockade prevented the detrimental renal hemodynamic effects of furosemide with suppression of aldosterone. Previous studies have also established beneficial renal hemodynamic and excretory function of AT1 receptor blockade in experimental models of CHF. Vople et al demonstrated that 6 weeks of AT1 blockade improve renal functional reserve in patients with mild CHF. Furthermore, the Val-HeFT and Charm studies have demonstrated that AT1 blockage can be added on safely in patient with stable CHF.

To protect the patients against the risk of hypotension, hyperkalemia, and increased plasma creatinine, the following measure are incorporated in the protocol:

- We will only include patients with compensated stable CHF as defined by; a) no change in NYHA symptoms over the past 3 months; b) on stable doses of ACE inhibitor, beta blocker, digoxin and furosemide over the past 4 weeks; c) no episode of decompensated CHF over the past 6 months. This will minimize their risk of fluid retention and congestion.
- We will exclude patients with prior diagnosis of intrinsic renal diseases including renal artery stenosis of > 50%
- We will exclude patients with Serum potassium of > 5.7 mEq/dL
- The protocol for Specific Aims 2 will be initiated in the CRU under close monitoring. Subjects will receive their first dose of study drug in the CRU. Thereafter, both blood pressure and heart rate will continue to be monitored for the next 4 hours. If the patients develop symptomatic hypotension as defined by systolic blood pressure of < 85 mmHg, with lightheadedness, dizziness or visual symptoms after the first dose of the medication in the CRU, the patient will be excluded from the rest of the study.
- Patients will have blood drawn to measure plasma creatinine and potassium 7-10 days after every dose increase until target dose is achieved. Thereafter, subjects will get blood draws every 4 weeks. *If there should be a potassium result <3.5 or >6.0, subjects will need to have labs redrawn the same day.*
- Subjects will also have access to a 24-hour phone number should they have any questions or develop any side effects.
- They will be instructed to measure their blood pressure weekly and record it, along with heart rate and weight.
- They will also receive a weekly phone call to review status.
- During the study, if patient develops symptomatic hypotension as defined above or an increased of plasma creatinine of > 0.3 mg/dL or hyperkalemia > 5.7 meq/ml, the dose will be reduced by 50%. If those parameters persist, the dose will be decreased further by 50%. At the discretion of the investigator, the medication can be discontinued

The following stopping rule will be applied to ensure patient safety

If the patients develop symptomatic hypotension as defined by systolic blood pressure of < 85 mmHg, with lightheadedness, dizziness or visual symptoms after the first dose of the medication in the CRU, the patient will be excluded from the rest of the study. During the study, if patient develops symptomatic hypotension as defined above or an increase in plasma creatinine of > 0.3 mg/dL or hyperkalemia > 5.7 meq/ml, the dose will be reduced by 50%. If those parameters persist, the dose will be decreased further by 50%. If those parameters persist, the subject will be withdrawn from the study

Other potential minor risk includes:

The risks of blood drawing include bleeding at the puncture site, bruising and pain. These risks occur in a very small portion of the population. We will exclude patients with hemoglobin of < 9 g/dL. The blood draw amount for this study is 200 mLs.

This protocol may be hazardous to an unborn child. There is no medical information to determine whether there are significant risks to a fetus carried by a mother who is participating in this study. Therefore, female

participants must be postmenopausal or have been surgically sterilized or have a negative pregnancy test and must agree to use a reliable double barrier method of contraception until study completion. A double barrier method of contraception is considered to be a combination of TWO of the following: birth control pill/implants/injections, intrauterine devices, spermicide, diaphragm or condoms.

Iothalamate contains a small amount of iodine and for persons allergic to iodine, this could pose a higher risk for an allergic reaction. To date in more than 5,000 patients, there have been only rare allergic reactions (one or two) when the solution has been used for this type of test. The amount of the material injected for this test will be approximately the same as used in a similar kidney function test performed on a routine basis (Approximately 250 test per month) in the Renal Function Laboratory. However, patients with a history of an allergic reaction to iodine should not participate in this study.

Adequacy of protection against risks

Recruitment and informed consent

Subjects will be recruited at the Mayo Clinic from the Heart Failure Clinic, Community Internal Medicine, General Internal Medicine, and past participants of [name] studies. In addition, we also now have in place a new web-based patient identification system developed at Mayo by the Cardiovascular Research Program. Upon identification of a subject, the study will be explained in detail by the investigators or study co-ordinator, the consent form reviewed, questions answered, and the consent form signed.

Potential benefits of the proposed research to the subjects and others

Subjects participating in specific aims 2 may potentially benefit from this study, with improved ventricular, renal and humoral function. More importantly, these studies will provide us new insights into the human cardiorenal syndrome that may allow us to develop new therapeutic strategies, which may benefit others with the same problem.

Importance of knowledge to be gained

This research will provide us new insights into the human cardiorenal syndrome that may allow us to develop new therapeutic strategies, which may benefit others with the same problem.

Data and safety monitoring plan

All clinical trial protocols carried out in the Mayo Clinic will have a Data Safety and Monitoring Plan incorporated into the protocol which will have to be reviewed and approved by Mayo Institutional Review Board (IRB). Our plan includes the formation of an internal safety monitoring committee consisting of 2 cardiologists: Dr [REDACTED] and Dr [REDACTED], and one nephrologist, Dr. [REDACTED]. All adverse and serious adverse events occurring between consent and final study visit will be reported to the safety monitoring committee, NIH and our IRB. Furthermore, the safety monitoring committee will review adverse events after 10 and 30 subjects have completed the protocol. The recommendations of the safety committee after each review will be submitted to the IRB. All serious adverse events will be reported as described below.

A plan for reporting Serious Adverse Events (SAE) to the IRB

A **Serious Adverse Event** is defined as an event with any of the following outcomes:

- Death
- Life-threatening adverse drug or device experience
- Inpatient hospitalization or prolongation of existing hospitalization
- Persistent or significant disability/incapacity

Unanticipated Problem Involving Risk to Subjects or Others (UPIRTSO):

Mayo Clinic's IRB and OHRP defines unanticipated problem/event involving risk to subjects or others (UPIRTSO) as any problem or event that was 1) serious; 2) unanticipated; AND 3) at least possibly related to the research procedures.

Serious: Serious problems/events can be well defined and include death; life threatening adverse experience; hospitalization: inpatient, new, or prolonged; disability/incapacity: persistent or significant; birth defect/anomaly; and/or per protocol OR may be problems/events that in the opinion of the local Investigator may have adversely affected the rights, safety, or welfare of the subjects or others, or substantially compromised the research data.

[figure not shown]
Unanticipated: (unexpected) problems/events are those that are not already described as potential risks in the consent form, not listed in the Investigator's Brochure, or not part of an underlying disease. A problem/event is "unanticipated" when it was unforeseeable at the time of its occurrence. A problem/event is "unanticipated" when it occurs at an increased frequency or at an increased severity than expected.

Related: A problem/event is "related" if it is possibly, probably or definitely related to the research study

Mayo IRB

Regardless of causality, the investigator will report SAE to DSMB within 72 hours of knowledge of the event to determine the relationship between the event and the study intervention. If the event was definitely related, probably related or possibly related to the study intervention, the PI will submit the UPIRTSO form to Mayo IRB within 72 hours, and include any relevant documents such as medical record notations or reports with the name and medical record number of the individual removed. Assess whether protocol modifications are required as a result of the UPIRTSO. The Investigator must provide an explanation on the UPIRTSO form explaining what corrective actions have already been taken.

The following section is the Mayo IRB's policy for handing a UPIRTSO report:

3. The names and contact information for study personnel to be contacted in the event of questions regarding adverse events and serious adverse events among study participants.

Subjects can call [name], telephone [REDACTED], at any time about any question on the studies including adverse events and serious adverse events.

REFERENCES

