After an equilibration period of 45 minutes, urine and blood samples are collected at 30-minute intervals for 3 periods to determine the baseline GFR and urinary sodium excretion (UNaV). Blood pressure will be measured at 20-minute intervals by using automatic blood pressure cuff, and heart rate will be continuously monitored. Urinary samples for determination of volume, sodium, potassium, lothalamate, and PAH, will be obtained at the end of each clearance period. Venous blood samples for lothalamate, PAH and sodium will be obtained at the middle of each clearance period. During the first clearance, venous blood samples for renin, aldosterone, angiotensin II, ACE, ACE 2, angiotensin 1-7, ANP, BNP, Bradykinin, NO, DNA, protein and cGMP will be obtained and urine samples for cGMP will also be obtained. BUN will also be run. Echocardiography will be performed after these baseline clearances as described.

At the completion of the baseline assessments, subjects will be randomized to Candesartan or placebo group. The randomization schedule will be provided by the Division of Biostatistics, implemented by the Mayo Pharmacy and administered by the CRU staff. The investigators and the CRU staff will not be aware of the randomization arm the subject is assigned to.

Subjects will receive the first dose of study drug in the CRU. Subjects will be started at 4 mg once a day. Thereafter, both blood pressure and heart rate (by electrocardiography) will continue to be monitored for the next 4 hours. If the patients develop symptomatic hypotension as defined by systolic blood pressure of ≤ 85 mmHg, with lightheadedness, dizziness or visual symptoms after the first dose of the medication in the CRU, the patient will be excluded from the rest of the study. The dose will be doubled every 14-18 days as tolerated to a goal of 16 mg a day or highest dose tolerated. Patients will get blood draw 7-10 days after each dose increase to measure plasma creatinine and potassium until target dose is achieved. *If there should be a potassium result <3.5 or >6.0 , subjects will need to have labs redrawn the same day.* Thereafter, subjects will get blood draws every 4 weeks (± 3 days). If distance indicates, blood draws will be arranged at the participants local clinic. Subjects will also have access to a 24-hour phone number should they have any questions or develop any side effects. They will be instructed to measure their blood pressure weekly and

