record it, along with heart rate and weight. They will also receive a weekly phone call to review status. During the study, if patient develops symptomatic hypotension as defined above or an increase of plasma creatinine of > 0.3 mg/dL or hyperkalemia > 5.7 meq/ml, the dose will be reduced by 50%. If those parameters persist, the dose will be decreased further by 50%. At the discretion of the investigator, the medication can be discontinued.

At the end of the twelve-week study period (± 7 days), subjects will be admitted to the CRU again. A 6-min walk, MLHFQ, echocardiography, renal clearance, humoral determination and renal functional reserve will be performed in the same manner as the baseline study. Subjects will also perform a 24-hour urine collection the day prior to their return visit for determination of sodium excretion, creatinine clearance and microalbuminuria. Subjects will be dismissed after the renal clearance study.

iii) Sample size and statistical analysis

The sample size calculation and statistical analysis have been designed in collaboration with the Division of Biostatistics, ([name] and [name]).

The **primary analysis** for this study will be a comparison of the parameters of interest between the AT1 receptor blockade group and placebo. This analysis will be completed using a two-sample t-test comparing the change from baseline to the latest time point available. In addition to this primary analysis, if complete or near complete data is available, a secondary analysis will be completed using all data from baseline to the latest available time point. The groups will be compared in this analysis using a 2 factor repeated measures analysis of variance. Values will be expressed as the mean \pm SE. A statistically significant difference will be considered to be present when $p<0.05$.

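### No creatinine or potassium draw is scheduled after a lab-triggered dose cut, although the second halving and the withdrawal depend on whether the abnormality persists

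*Combined protocol and SAP*

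**What the plan says.** The Study protocol section sets the titration: "Subjects will be started at 4 mg once a day", and then "The dose will be doubled every 14-18 days as tolerated to a goal of 16 mg a day or highest dose tolerated".

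Laboratory monitoring has three parts, given in that section and repeated under Potential risks and Protection against risk:

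- During titration: "Patients will get blood draw 7-10 days after each dose increase to measure plasma creatinine and potassium until target dose is achieved".
- After that, draws every 4 weeks, with a window of 3 days either side in the Study protocol section.
- A same-day redraw when potassium is below 3.5 or above 6.0.

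The response to an abnormal result is a ladder. For "an increase of plasma creatinine of > 0.3 mg/dL or hyperkalemia > 5.7 meq/ml, the dose will be reduced by 50" per cent. Next, "If those parameters persist, the dose will be decreased further by 50" per cent. The Study protocol section ends the ladder with "At the discretion of the investigator, the medication can be discontinued". The stopping rule in the risk section adds a third rung: if the abnormality still persists after the second cut, the subject is withdrawn.

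Neither section dates a creatinine or potassium draw from a dose reduction.

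**The concern.** Whether a laboratory abnormality has persisted can be known only from another laboratory result. The second and third rungs of the ladder therefore depend on a test that the schedule does not place. Symptomatic hypotension, the other trigger, is not affected in the same way, because weekly home blood pressure and weekly phone calls follow it.

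The matter is patient safety. The risk section's main worry is that adding candesartan "would result in hypotension, hyperkalemia, and increased plasma creatinine", and these draws are the scheduled check on the last two. Subjects already take an ACE inhibitor and may take an aldosterone antagonist. They may enter with a calculated clearance just above 20 ml/min and a potassium as high as 5.7, the level above which the dose is cut. If the abnormality does not resolve at half dose, a subject could stay on drug for weeks before any scheduled result prompts the next step.

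**Working it through.** The plan gives no figure to reproduce, so the check is a day count on its stated windows.

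**Inputs** (Study protocol section): 4 mg on day 0; doubling every 14-18 days to 16 mg, hence two doublings; titration draw 7-10 days after an increase; later draws every 28 ± 3 = 25 to 31 days; final visit at 84 ± 7 = day 77 to 91.

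**Assumptions:** the step to 16 mg gets its own 7-10 day draw; each cut is made on the day of the draw that prompts it; no unscheduled test is ordered. The text does not say where the 4-weekly clock starts, so both readings are shown.

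**1. Reaching 16 mg.** 2 × 14 = day 28 to 2 × 18 = day 36.

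**2. Draw at 16 mg, where the first cut is made.** 28 + 7 = day 35 to 36 + 10 = day 46.

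**3. Later scheduled draws.**

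| | Clock from reaching 16 mg | Clock from the 16 mg draw |
|---|---|---|
| Wait after first cut | 25 − 10 = 15 to 31 − 7 = 24 days | 25 to 31 days |
| Second cut decided | 28 + 25 = day 53 to 36 + 31 = day 67 | 35 + 25 = day 60 to 46 + 31 = day 77 |
| Withdrawal decided | 53 + 25 = day 78 to 67 + 31 = day 98 | 60 + 25 = day 85 to 77 + 31 = day 108 |

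Set against a final visit on day 77-91, the withdrawal step comes around or after the end of treatment on either reading.

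**4. With a recheck 7-10 days after each cut.** Second cut: 35 + 7 = day 42 to 46 + 10 = day 56. Withdrawal: 42 + 7 = day 49 to 56 + 10 = day 66. The first recheck comes 15 − 10 = 5 to 24 − 7 = 17 days sooner on the first clock, or 25 − 10 = 15 to 31 − 7 = 24 days sooner on the second.

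**5. Does the same-day redraw fill the gap?** Compare the triggers:

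| Result | Dose cut | Same-day redraw |
|---|---|---|
| Creatinine rise above 0.3 mg/dL alone | yes | no |
| Potassium above 5.7, up to 6.0 | yes | no |
| Potassium above 6.0 | yes | yes |

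Two of the three results that prompt a cut prompt no redraw. In the third, a sample taken the same day cannot show what the lower dose has done.

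**6. Two wording points in the titration rule.** If the 4 mg start counts as a dose increase, the first on-drug draw is on day 7-10, which is 14 − 10 = 4 to 18 − 7 = 11 days before the first doubling. If it does not, the first draw is 14 + 7 = day 21 to 18 + 10 = day 28, after the doubling on day 14-18. If the phrase about reaching target excludes the step to 16 mg, the first scheduled draw at that dose is day 53-67 instead of day 35-46.

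**The case against.** The strongest reply is that protection begins at once: the abnormal result itself halves the dose, so the subject spends the wait on half the dose. A rule about persistence also implies a repeat test, and the plan leaves its date to the investigator, who may discontinue the drug. Doubling is only as tolerated. Weekly calls and a 24-hour phone line run alongside. A laboratory abnormality that raises risk is itself a ground for exclusion, and a safety committee that includes a nephrologist receives adverse events. The documents give no rate for these events, so the number of subjects affected cannot be computed.

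All of that stands, and it limits the point to a delay in the second and third steps. It does not remove the point, because none of these safeguards sets a date for a laboratory test after a cut.

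Three stronger readings are tempting but not supported:

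- *Draws follow dose increases only.* The 4-weekly draws and the potassium redraw contradict this.
- *Every subject is doubled before any on-drug laboratory result.* This holds only if the 4 mg start is not a dose increase. The text does not say so, and going from no drug to 4 mg can fairly be read as one. It is an ambiguity, not a demonstrated omission.
- *A subject cut at 8 mg has no scheduled draw until week 12.* Counting from the day 21-28 draw, that would be 77 − 28 = 49 to 91 − 21 = 70 days. It requires that only 16 mg counts as the target. The titration goal also allows the highest tolerated dose, and on that reading the 4-weekly draws apply.

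**Conclusion.** The concern holds in a limited form. The plan makes two safety actions depend on whether a creatinine or potassium abnormality persists, and schedules no draw after a dose cut to find out. For a cut at 16 mg, the scheduled wait is about two to three and a half weeks, or three and a half to four and a half weeks, depending on where the 4-weekly clock starts. Two such waits bring the withdrawal step to the end of the 12-week period or beyond, so on scheduled draws alone the last rung can protect few subjects or none who are first cut at that draw.

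This rests on the assumptions listed with the day count, above all that the site orders nothing unscheduled. Many investigators would retest earlier, but the plan does not require it. The treatment of the 4 mg start and of the final step to 16 mg is a minor matter of wording.

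**What to change.** In the Study protocol section, in the matching bullets under Potential risks and Protection against risk, and in the stopping rule:

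- Require creatinine and potassium 7-10 days, or sooner, after every dose reduction.
- State that this draw decides persistence for the two laboratory criteria.
- As a clarification, state that the 4 mg start and the step to 16 mg each count as a dose increase for the 7-10 day draw, and that the result is reviewed before the next doubling.

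The cost is a wording amendment and one extra draw per reduction. If not already covered, add at most one draw per subject for the start (76 in all) and one for each subject who reaches 16 mg. Draws at a local clinic are already allowed. The 200 mL blood amount stated in the risk section should be checked against the added draws.

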Subjects who are already taking AT1 receptor blocker will be excluded. Aldosterone antagonist, antiarrhythmic medications and other vasodilators will be allowed; however, all cardiac medications must be at stable doses 4 weeks prior to initial testing visit. Subjects taking nonsteroidal anti-inflammatory drugs (NSAIDs) except aspirin will not be able to increase their medication dose for the duration of the study. Subjects will be excluded if they have had a prior diagnosis of intrinsic renal disease, including renal artery stenosis of > 50%, or if they meet any one of the exclusion criteria listed below.

Exclusion criteria specification

- Prior diagnosis of intrinsic renal diseases including renal artery stenosis of > 50%
- Peritoneal or hemodialysis within 90 days or anticipation that dialysis or ultrafiltration of any form will be required during the study period
- Hospitalization for decompensated CHF during the past 6 months
- Subjects that are taking AT1 receptor blockers
- Myocardial infarction within 6 months of screening
- Unstable angina within 6 months of screening, or any evidence of myocardial ischemia
- Significant valvular stenosis, hypertrophic, restrictive or obstructive cardiomyopathy, constrictive pericarditis, primary pulmonary hypertension, or biopsy proven active myocarditis
- Severe congenital heart diseases
- Sustained ventricular tachycardia or ventricular fibrillation within 14 days of screening
- Second or third degree heart block without a permanent cardiac pacemaker
- Stroke within 3 months of screening, or other evidence of significantly compromised CNS perfusion
- ALT >1.5 times the upper limit of normal
- Serum sodium of < 125 mEq/dL or > 160 mEq/dL
- Serum potassium of < 3.5 mEq/dL or > 5.7 mEq/dL
- Serum digoxin level of > 2.0 ng/ml
- Hemoglobin < 9 gm/dl
- Other acute or chronic medical conditions or laboratory abnormality which may increase the risks associated with study participation or may interfere with interpretation of the data
- Received an investigational drug within 1 month prior to dosing

- Patients with an allergy to iodine.
- Female subject who is pregnant or breastfeeding
- In the opinion of the investigator, is unlikely to comply with the study protocol or is unsuitable for any reasons

ii) **Study protocol**

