After enrollment into the study, diet instructions will be given by a dietitian about a no added salt diet, 2-3 gm salt/day and 0.75 gm protein/Kg/day diet which will be maintained throughout the study period. Baseline chemistry, ALT and complete blood count will be obtained and subjects taking NSAIDs except for aspirin will not increase their dose until the end of the study. A urine pregnancy test will be performed, if necessary.

Twenty-four hour urine collection will be obtained one day prior to the active renal clearance study day for assessment of sodium excretion, creatinine clearance and microalbuminuria. Sulfa containing medications and Probenecid will be withdrawn for 72 hours prior to the active renal clearance study days. Patients will be instructed to avoid strenuous physical activity and to abstain from smoking and alcohol-containing drinks three days prior to active renal clearance study day.

After the three-week stabilization period subjects will fast overnight and be admitted to the CRU on the morning of the active study day where they will undergo a 6 min walk. Their first urine void after admitting will be collected for protein analysis and urine pregnancy test (if necessary). They will complete the Minnesota Living with Heart Failure Questionnaire (MLHFQ) during their stay. Their usual morning dose of medications (except diabetic medications) will be taken at 07:00 upon admission. The subjects will be placed in the supine position for 1 hour. During the first 15 minutes, two standard intravenous (IV) catheters will be placed (one in each arm). One catheter will be used for infusion and the other (in the contralateral arm) for blood sampling.

Subjects will be asked to drink 5 mL/Kg of water initially and then drink the amount equal to the urine output every 30 minutes to ensure sufficient urinary flow. A priming dose of lothalamate (0.0053 mL/Kg) to measure glomerular filtration rate (GFR) will be infused, followed by a constant rate IV sustaining dose (calculated according to estimated kidney function) of lothalamate to achieve steady-state plasma concentrations of 15 to 20 mg/L. The subjects will be asked to empty their bladder spontaneously every thirty minutes.

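### On the plain wording, no potassium or creatinine value is scheduled on the 4 mg starting dose before the first doubling to 8 mg

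*Combined protocol and SAP*

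**What the plan says.** The titration and laboratory schedule is in the combined protocol and SAP, Research Design and Methods, part ii (Study protocol).

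- Start: "Subjects will be started at 4 mg once a day". The first dose is given in the CRU, followed by 4 hours of blood pressure and heart rate monitoring.
- Titration: "The dose will be doubled every 14-18 days as tolerated to a goal of 16 mg a day or highest dose tolerated".
- Titration laboratory draws: "Patients will get blood draw 7-10 days after each dose increase to measure plasma creatinine and potassium until target dose is achieved". After that, draws are every 4 weeks (± 3 days).
- Dose reduction: the dose is halved for symptomatic hypotension, for "an increase of plasma creatinine of > 0.3 mg/dL", or for potassium above 5.7. It is halved again if the problem persists.
- Other contact on treatment: a weekly phone call, a 24-hour phone number, and weekly home blood pressure, heart rate and weight.

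The section on potential risks and protection against risk repeats the draw rule in nearly the same words. It lists the draws among the measures that guard against hypotension, hyperkalemia and increased creatinine.

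Before treatment, baseline chemistry is taken after enrollment. A 24-hour urine collection for creatinine clearance is made the day before the CRU study. The blood samples listed for the CRU day itself do not name potassium or creatinine: "Venous blood samples for lothalamate, PAH and sodium will be obtained at the middle of each clearance period", with hormones and BUN added.

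**The concern.** The draw rule is triggered by an increase, and the protocol describes 4 mg as the start and the later steps as doublings. The first increase is therefore the step from 4 to 8 mg, and the first scheduled draw comes after it. The plan puts a laboratory check ahead of the second doubling but not ahead of the first.

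The population makes this matter. Subjects are on an ACE inhibitor, creatinine clearance may be as low as just above 20 ml/min, and "Aldosterone antagonist, antiarrhythmic medications and other vasodilators will be allowed". Entry excludes potassium only above 5.7, the same number that triggers a dose reduction, so a subject may start with no headroom. A rise in potassium or creatinine can be silent, and neither a phone call nor a home blood pressure reading would show it. A subject over a laboratory limit on 4 mg should have the dose cut under the plan's own rule, but on schedule the dose is doubled.

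**Working it through.** The plan gives no stated figure to reproduce, so the check is calendar arithmetic from the first dose (day 0).

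**Inputs** (all from Study protocol): start 4 mg; doubling interval 14-18 days; target 16 mg, hence two doublings; draw 7-10 days after each increase; treatment 12 weeks = 84 days.

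**Plain reading (the first increase is 4 to 8 mg)**

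| Event | Calculation | Day |
|---|---|---|
| First doubling, to 8 mg | one interval | 14-18 |
| First scheduled draw, on 8 mg | 14 + 7 to 18 + 10 | 21-28 |
| Second doubling, to 16 mg | 2 × 14 to 2 × 18 | 28-36 |
| Second scheduled draw, on 16 mg | 28 + 7 to 36 + 10 | 35-46 |

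- Time before the first scheduled value: 14-18 days on 4 mg plus 7-10 days on 8 mg, that is 21-28 days. As a share of treatment, 21/84 = 25% to 28/84 = 33%.
- Scheduled on-treatment values before the first doubling: none. Before the second doubling: one.
- Margin from that draw to the second doubling: 14 − 10 = 4 to 18 − 7 = 11 days.
- For a subject over a laboratory limit on 4 mg, the reduction rule gives 4 × 0.5 = 2 mg and the schedule gives 4 × 2 = 8 mg.

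**Alternative reading (starting 4 mg counts as an increase)**

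The first draw falls at day 7-10, again 4-11 days before the first doubling, and the gap closes.

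**Subject held at 4 mg**

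There is no increase, so on the plain reading no titration draw is triggered. The goal is 16 mg or the highest tolerated dose, so the four-weekly draws can apply, but the text does not date their start for such a subject.

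**How many subjects?**

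The documents give neither a potassium distribution nor an expected rise on 4 mg. An illustration with assumed inputs shows how little can be said: entry potassium normal, truncated to 3.5-5.7, mean 4.3-4.7, between-subject SD 0.3-0.4; rise on 4 mg 0.2-0.4; within-subject SD 0-0.3 (mEq/L). The share of candesartan subjects above 5.7 then runs from 0.003% to 11.0%, or about 0 to 4 of 38. That range is too wide to support a count. Creatinine was not modelled.

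**The case against.** The strongest reply is that going from nothing to 4 mg is itself an increase, and that the protocol speaks of each (in the risk section, every) increase without excluding the first. Site staff could reasonably draw at day 7-10 on that basis. This stands as a possible reading, so it would be too strong to say that the sponsor definitely intended no draw on 4 mg. It is still the less literal reading: the text separates starting from doubling, and neither statement of the rule mentions a draw after the first dose. A safety draw should not depend on that choice.

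A second reply points to the other safeguards. Chemistry is taken at enrollment, potassium above 5.7 is excluded, and a confirmatory creatinine clearance is required. Weekly calls, the 24-hour line and home blood pressure continue through treatment. Doubling is only as tolerated, unscheduled tests are not barred, and the investigator may stop the drug. The safety committee reviews adverse events after 10 and 30 completers. All of this bears on severity, but none of it is a scheduled potassium or creatinine on 4 mg.

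A reader might also infer from the CRU-day sample list that no creatinine is available close to the first dose. The documents do not support that: the 24-hour creatinine clearance collected the day before implies a blood creatinine at about that time. The same cannot be said of potassium.

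**Conclusion.** The point holds on the plain wording. A subject titrated on schedule is doubled to 8 mg at day 14-18 without a scheduled on-treatment potassium or creatinine, and the first arrives at day 21-28. The laboratory dose-reduction rules cannot act on scheduled data before that doubling, and no other section closes the gap.

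The harm is bounded. The dose reached without a scheduled check is 8 mg, half the target, for 7-10 days, and a lasting rise is found before 16 mg. A reader might infer that a known number of subjects would be harmed, or that the trial runs without laboratory safety monitoring. The documents support neither: the frequency cannot be derived from them, and both pre-treatment chemistry and later draws are planned.

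The conclusion rests on two assumptions: that the first dose is not counted as an increase, and that titration follows the stated intervals. If the first of these is wrong, what remains is unclear wording and the absence of any explicit rule that a result must be seen before the dose is doubled. The change should be made; confidence is medium because of the alternative reading.

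**What to change.** In both places where the draw rule appears (Study protocol, and the risk-protection section), write:

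*Plasma creatinine and potassium are drawn 7-10 days after the first dose and 7-10 days after each dose increase; the dose is not doubled until the latest result is known and is below the dose-reduction limits.*

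This gives the first doubling the 4-11 day margin that the second already has. It also gives a subject held at 4 mg a dated on-treatment value.

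Cost: one small draw per subject in both arms, at most 38 + 38 = 76. The protocol already allows this away from the centre: "If distance indicates, blood draws will be arranged at the participants local clinic". A few doublings will be held, some of them in placebo subjects through ordinary variation, so slightly fewer subjects may reach 16 mg. If the first dose was already meant to trigger a draw, the new wording only makes that explicit, and the hold rule is the new element.

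Optional: a pre-dose potassium on the CRU day. It needs no extra puncture, because a sampling line is already in place: "One catheter will be used for infusion and the other (in the contralateral arm) for blood sampling".
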